4.5.3.2 Liver Monitoring

The following parameters will be investigated in addition to the standard lab presentations:

Version 2.0 Page: 37 of 57

- Aspartate aminotransferase (AST) (in U/L),
- Alanine aminotransferase (ALT) (in U/L),
- Alkaline phosphatase (ALP) (in U/L),
- Total bilirubin in serum (TB) (in mg/dL)
- International normalized ratio (INR).

Frequency tables, presenting number and percentage of participants, by treatment group for baseline and post-baseline (scheduled and unscheduled measurements) will be presented for the following categorizations (where ULN stands for "Upper Limit of Normal"):

- For ALT and AST, separately:
 - \circ $\geq 1 \times ULN, \geq 3 \times ULN, \geq 5 \times ULN, \geq 8 \times ULN, \geq 10 \times ULN, \geq 20 \times ULN$
- For ALT and AST combined (if at least one of ALT and AST falls into the category):
 - $\circ \geq 3 \times ULN, \geq 5 \times ULN, \geq 8 \times ULN, \geq 10 \times ULN, \geq 20 \times ULN$
- For TB:
 - $\circ \ge 1 \times ULN, \ge 2 \times ULN, \ge 5 \times ULN, \ge 8 \times ULN$
- For ALP:
 - $\circ \geq 1.5 \times ULN, \geq 2.0 \times ULN, \geq 3.0 \times ULN$
- For INR:
 - >1.5, >2

Frequency tables presenting number and percentage of participants by treatment group for post-baseline (scheduled and unscheduled measurements) will be presented for the following combinations of ALT/AST and TB or INR,

Relative to ULN:

- ALT or AST $\ge 3 \times ULN$ and $\ge 1.5 \times ULN$ in TB
- ALT or AST $\geq 3 \times ULN$ and $\geq 2 \times ULN$ in TB
- ALT or AST $\ge 3 \times ULN$ followed by $\ge 2 \times ULN$ in TB (measured within 30 days afterwards) (Hy's Law criteria).
- (ALT or AST $\geq 3 \times ULN$) and ≥ 1.5 for INR
- ALT or AST \geq 5×ULN for more than 2 weeks
- ALT or AST $\geq 8 \times ULN$
- ALT or AST ≥ 3×ULN with the appearance of any signs or symptoms on liver event clinical signs and symptoms eCRF page
- ALP $\geq 2 \times ULN$ and TB $\geq 2 \times ULN$

Relative to baseline (BL):

• (ALT $\ge 3 \times BL$ or AST $\ge 3 \times BL$) and TB $\ge 2 \times BL$

Version 2.0 Page: 38 of 57

- ALT $\ge 3 \times BL$ or AST $\ge 3 \times BL$
- ALT \geq 5×BL or AST \geq 5×BL
- (ALT $\ge 2 \times BL$ or AST $\ge 2 \times BL$) and TB $\ge 2 \times BL$
- ALP $\ge 2 \times BL$ and TB $\ge 2 \times BL$

Time to event analysis

Cumulative incidence estimates for the time to first occurrence of ALT \geq 3×ULN and first occurrence of ALP \geq 3×ULN will be derived. If no such an increase is observed, the observation is censored at the last visit date. Tables with the number of participants under risk, cumulative number of participants with ALT \geq 3×ULN and ALP \geq 3×ULN, and estimated probability for an event including 95% CIs (two-sided) will be presented. Furthermore, cumulative incidence curves will be provided by treatment group. If a participant does not have any post-baseline data, she will be censored at baseline.

Figures

Hepatocellular DILI screening plot will be displayed to identify cases of possible serious hepatocellular DILI. In the plot each patient is plotted based on their maximum postbaseline TB (y-axis) and transaminase values (ALT or AST, whichever is higher). Together with the plot, a frequency table for patients in each quadrant (Potential Hy's Law, Cholestasis, Temple's corollary) will be shown.

Cholestatic drug-induced liver injury screening plot will be shown to identify significant ALP elevation in the setting of hepatic dysfunction. Maximum postbaseline TB is plotted against maximum postbaseline ALP. Similar to above, a frequency table for patients in each quadrant (TB \geq 2xULN and ALP \geq 2xULN, TB \geq 2xULN and ALP \leq 2xULN and ALP \leq 2xULN will be shown.

Individual patient presentations

If a participant meets the criteria for close liver observation (as specified in Section 10.5.1 of the protocol) at any time point, a plot for her individual time course in the following laboratory parameters will be presented: 1) ALT, AST, TB, and ALP relative to ULN over time and 2) absolute values for INR over time. It will be indicated within the plot on which days the study drug was taken (i.e. start and stop dates of treatment intake), in addition all AEs and CM 6 months (182 days) prior to the first onset of close liver observation will be shown in the plot 1. Furthermore, listings will be provided for INR (absolute values) and for liver-related parameters, i.e. ALT, AST, TB, ALP, GGT, direct bilirubin, CK and LDH (with results relative to ULN).

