1.3 Schedule of Activities (SoA)

SoA is presented in Table 1–2.

Table 1-2: Schedule of Activities

Period	Screening period ^a		Intervention period			FU period	
Visit name	SCR-1	SCR-2	BL	T1	T2	T3/ EoT ^{b,c}	FU
In person (IP) or phone visit	IP	IP	IP	IP	a	IP	~
Visit week	Pleas	e see foot		4	8	12	16
Visit day	-42 to -24 a	-10 a	1 ^a	29	57	85	113
Allowed window in days	Pleas	e see foot	note a	+7	+7	+7	+7
Baseline characteristics	3						
Informed consent	•						
Demography	•						
Medical history (includes substance usage)	•						
Check for prohibited medication washout (Section 10.7)	•	•	•				
Screening and randomi	zation		,		1	_	
Inclusion and	•	● d	•				
exclusion criteria	_						
IRT Screening	•	_	_				
IRT Screen fail (if applicable)	•	•	● e				
IRT Randomization			•				
Study medication and s	tudy exit						
Study medication dispensing/training			•				
Study medication			Starts on	Visit Day 1 e	vening	>	
Study medication						•	
collection (if							
applicable)							
Study intervention compliance				er the first do	•		
IRT for EoT			1			•	
Participant feedback						•	
survey (optional)							
Safety / laboratory	1	1	1				
Complete physical	•						
examination including							
height and weight							
Vital signs	•			•		•	
Blood samples	•			•		•	
(safety)							
Urine pregnancy test	•						
(if applicable,							
Section 8.3.4)							
Urinalysis	•			 		•	
Blood sample (PK)	1		ĺ	● f		● f	

21 SEP 2023 Page: 15 of 73

Table 1-2: Schedule of Activities

Period	Scre	ening per	riod ^a	Inter	vention p	eriod	FU period
Visit name	SCR-1	SCR-2	BL	T1	T2	T3/ EoT ^{b,c}	FU
In person (IP) or phone visit	IP	IP	IP	IP		IP	
Visit week	Please	e see foot	note a	4	8	12	16
Visit day	-42 to -24 a	-10 ^a	1 ^a	29	57	85	113
Allowed window in days	Please	e see foot	note a	+7	+7	+7	+7
Symptom-based				•		•	
physical examination							
AE (Section 8.4.1)		e-related only		er the first dos	-	medication	>
Prior and concomitant		-	•				
medication							>
Digital health technolog	y tools						
PSG ^g + Sleepiz	, .	•		•		•	
One+ (2 consecutive							
nights)							
Sleepiz One+ device		•					
dispensation and							
training							
Sleepiz One+ (at			l			L	
home)						>	
Sleepiz One+ device						•	
collection							
eDiary and eCOA instru	ıments						
Dispensation and	•						
training of							
participant's handheld							
device							
eC-SSRS	•			•		•	
SD (daily)						>	
HFDD (twice daily)						>	
PROMIS SD SF 8b h	•					>	
ISI	•		•	•		•	
GAD-7			•	•		•	

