PGI-S i						>	
PGI-C ^j		-	Starts 1	weeks after	BL		
Study medication			Starts after	er the first dos	se of study r	medication	
intake documentation						>	
Collection of						•	
handheld device							

AE = adverse event, BL = baseline, eCOA = Electronic clinical outcome assessments, EoT = End of Treatment, ePRO = Electronic patient-reported outcome, FU = follow-up, IP = In person, IRT = Interactive response technology, PK = pharmacokinetics, PSG = polysomnography, SCR = screening, SoA = Schedule of activities, T = treatment.

Questionnaires: eC-SSRS = Electronic Columbia-Suicide Severity Rating Scale, GAD-7 = Generalized Anxiety Disorder Scale -7, HFDD = Hot Flash Daily Diary, ISI = Insomnia Severity Index, PGI-C = Patient Global Impression of Change, PGI-S = Patient Global Impression of Severity, PROMIS SD SF 8b = Patient-reported Outcomes Measurement Information System Sleep Disturbance Short Form 8b, SD = Sleep Diary.

21 SEP 2023 Page: 16 of 73

- a All screening evaluations should typically be completed within 4–6 weeks with at least 14 days between SCR-1 and SCR-2 and at least 7 days at home after SCR-2 and before BL. The time required for scheduling for PSG and central reading of PSG needs to be considered for visit planning.
 b All EoT assessments (except for the safety and PK sample) are performed in the morning after the second night in the PSG lab.
- **c** If a participant discontinues prematurely from treatment, an EoT visit will be performed as soon as possible; it will comprise all assessments scheduled for the EoT visit. The EoT visit will be followed after 4 weeks by the FU visit. The handheld device will be collected at the last scheduled IP visit.
- d Eligibility check on inclusion criterion 3 (HFDD) should be assessed prior to PSG.
- e Including consultation about results obtained from screening procedures.
- f PK sample is collected on the second day in the PSG lab together with the safety lab sample.
- **g** All PSGs scheduled for T1 and T3 need to be performed under treatment, i.e., the second PSG night at EoT needs to be performed at the latest during the night after the last capsule has been taken.
- **h** The PROMIS SD SF 8b will be collected at SCR-1 and weekly from BL until EoT.
- i The PGI-S will be collected weekly from SCR-2 until EoT.
- j The PGI-C will be collected weekly following the PGI-S from 1 week after BL until EoT.

2. Introduction

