4.5.3.1 Laboratory Data

The number of participants with treatment-emergent (i.e., 14 days from the last treatment intake) high or low abnormal laboratory values will be summarized for each laboratory parameter by study treatment. Both scheduled and unscheduled laboratory measurements will be considered.

Continuous laboratory parameter values including the change from baseline will be summarized by visit and study treatment. Frequency tables for categorical laboratory parameter will be summarized by visit and study treatment.

Central laboratory will be considered for descriptive analysis. Local laboratory measurements will be listed, if available.

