6.1 APPENDIX 1: Population Characteristic

6.1.1 Participant Disposition

The number of participants enrolled, randomized and valid for the FAS, SAF and SLAS will be summarized overall and by study treatment and study site.

The number of participants randomized will further be summarized by country/region and by study treatment and overall.

The number of sites will be summarized by country/region.

The number of participants with important protocol deviations and the number of screen failures will be summarized overall and by study treatment, country/region and study site.

The number of participants per important deviation category and validity finding will be presented by study treatment and overall.

A disposition summary will be presented summarizing the number of participants starting and completing each study period (screening, treatment, follow-up), the number of participants discontinuing it and the primary reason for discontinuation. This will be presented overall and for each study treatment. The number of participants completing the overall study will be provided by study arm and overall. Participants who completed the study are those who complete study treatment and were followed for the duration of the study. Follow-up is considered to be completed if the participants complete the follow-up visit.

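### The ALT and ALP time-to-event analysis censors event-free women at the last visit, usually about 4 weeks after their last scheduled liver test, so untested time is shown as liver follow-up; the effect on the estimate is small.

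*SAP*

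**What the plan says.** SAP 4.5.3.2 (Liver Monitoring, time to event analysis) plans "Cumulative incidence estimates for the time to first occurrence of ALT" of at least 3×ULN, and the same for ALP. It asks for numbers under risk, cumulative event counts, estimated probabilities with 95% intervals, and curves by treatment group. Two censoring rules are given:

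- For women without an event: "If no such an increase is observed, the observation is censored at the last visit date".
- As a fallback: "If a participant does not have any post-baseline data, she will be censored at baseline".

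The schedule of activities (Protocol 1.3, Table 1-2) marks safety blood samples at SCR-1, T1 (Week 4) and T3/EoT (Week 12) only. It marks none at T2 or at follow-up (FU), and FU is not marked as an in-person visit. Footnote f fixes the timing of the blood draw: "PK sample is collected on the second day in the PSG lab together with the safety lab sample". Footnote c covers premature discontinuation: "The EoT visit will be followed after 4 weeks by the FU visit". SAP 6.1.1 treats FU as a visit in its own right: "Follow-up is considered to be completed if the participants complete the follow-up visit".

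For comparison, SAP 4.5.3.1 limits its laboratory table to "treatment-emergent (i.e., 14 days from the last treatment intake) high or low abnormal laboratory values". The time-to-event paragraph sets no such limit.

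**The concern.** An ALT or ALP rise can be seen only when blood is drawn. A woman should therefore count as under observation for these events up to her last liver test, not up to a later contact at which nothing is measured. Under the planned rule, an event-free woman who attends FU stays at risk for about 4 further weeks.

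Two things follow. First, the number-at-risk table shows nearly all completers under liver observation after treatment, and the flat curve could be read as evidence of no late rise. The design schedules no test that could provide that evidence. Second, a woman who stopped early can sit in the denominator at a draw for which she gave no sample, which lowers the estimate. If early stopping differs between arms, so does the lowering.

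Liver enzyme increase is a named risk in Protocol 2.3.1, and any condition triggering close liver observation is an adverse event of special interest (Protocol 8.4.6). The display should therefore mean what it appears to mean.

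**Working it through.** **Inputs.** Visit days are T1 = 29, T2 = 57, T3/EoT = 85 and FU = 113, each with a +7-day window (Protocol Table 1-2). The EoT safety sample is taken on the second day in the sleep laboratory, about day 85–86 (footnote f). About 39 women are randomized per arm (SAP 5).

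**1. The plan's own interval.** FU − EoT = 113 − 85 = 28 days, which is the 4 weeks of footnote c. With the sample on day 86 it is 113 − 86 = 27 days. Across the visit windows it runs from 113 − 92 = 21 to 120 − 85 = 35 days. As a share of displayed follow-up, 28/113 = 24.8% (27/113 = 23.9%).

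**2. Completers.** A cumulative incidence estimate changes only at event times. The tail lies after the last scheduled test, so it does not move the estimate. It changes only the number at risk and the length of the flat curve.

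**3. Who dilutes the estimate.** An early stopper has her last sample at EoT and is censored at EoT + 28 days. She is wrongly in the risk set at the Week 4 draw (day 29) only if her EoT falls in about days 1–28, and at the Week 12 draw (day 85) only if it falls in about days 57–84. With EoT on day 40, FU is on day 68 and no scheduled draw lies between. Similarly, a woman whose last contact is T2 has 57 − 29 = 28 untested days, but these cover no scheduled draw.

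**4. Size at Week 4.** The documents give no rate of early stopping, so this is an assumed range, with one event at the Week 4 draw:

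| Stoppers before Week 4, of 39 | Last-visit censoring | Last-test censoring | Difference |
|---|---|---|---|
| 2 | 1/39 = 2.56% | 1/37 = 2.70% | 0.14 points |
| 4 | 1/39 = 2.56% | 1/35 = 2.86% | 0.29 points |

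With 4 stoppers the ratio is 35/39 = 0.90. For scale, the standard error of 1/39 is about √(0.0256 × 0.9744/39) = 2.5 percentage points. If the 4 stoppers have their EoT sample on day 20 and FU on day 48, and the event falls on nominal day 85, both rules give 1/35 = 2.86%.

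**5. Does simply moving the censoring date work?** Assume 39 women, no early stoppers, one event at EoT, and test days spread evenly over days 85–92. If the event is found on a day when a fraction j/8 of the others are still to be tested or are tested that day, the expected estimate is [1 − (1 − j/8)^39] / (39j/8):

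| j | 1 | 2 | 3 | 4 | 5 | 6 | 7 | 8 |
|---|---|---|---|---|---|---|---|---|
| Estimate | 20.4% | 10.3% | 6.8% | 5.1% | 4.1% | 3.4% | 2.9% | 2.6% |

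The average is about 7.0%, against a true proportion of 1/39 = 2.6%. Women already tested normal leave the risk set before the late test. With times grouped by nominal visit, all 39 count at Week 12/EoT and the estimate is again 1/39 = 2.6%.

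**The case against.** The strongest objection is that the planned rule does little harm and the obvious replacement does more. Step 5 bears this out for exact-day censoring at the last test: at EoT, one of only two scheduled post-baseline draws, last-visit censoring does better. This stands, and it determines the form of the fix. It does not justify last-visit censoring, because grouping by visit removes the instability and still takes unsampled women out of the risk set.

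Three stronger readings are tempting, and the documents do not support them:

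- A reader might infer that, because about a quarter of displayed follow-up is untested, the estimates are off by a similar amount. They are not: the SAP plans no rate per person-time here, and completers' tails leave the cumulative incidence unchanged.
- A reader might infer that the two censoring rules contradict each other. The baseline rule is a fallback for a woman who contributes nothing after baseline and can stand beside the main rule. What is missing is a definition of post-baseline data, which could mean any data or ALT/ALP data.
- A reader might infer that a liver signal would be hidden. SAP 4.5.3.2 also tabulates threshold crossings as counts and percentages with unscheduled measurements included, and adds liver-injury screening plots, individual profiles and listings. Protocol 8.3.3 and 10.5 require repeat tests once a value is abnormal.

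**Conclusion.** The point holds as a minor one. The planned rule counts about 4 weeks without a scheduled liver test as event-free liver follow-up for women who attend FU. It also keeps some early stoppers in the denominator at a draw they did not have.

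The visible consequence is in the number-at-risk table and the curve after about day 92. The numerical consequence is 0.1 to 0.3 percentage points in the assumed example (2 to 4 of 39 women stopping before Week 4, one event at Week 4) and none from completers' tails. It does not apply to every early stopper, only to those whose last sample falls in roughly days 1–28 or 57–84 and who then attend FU.

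This rests on reading the last visit literally as FU, which the SAP does not restrict, and on FU having no scheduled blood sample. Unscheduled tests after EoT would shorten the untested period for the women who have them. The analysis is descriptive, no hypothesis is tested, and the primary endpoint is untouched.

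**What to change.** Replace the two censoring sentences in SAP 4.5.3.2 with wording such as: *A participant without such a rise is censored at her last post-baseline ALT (respectively ALP) measurement, scheduled or unscheduled, or at baseline if she has none. Event and censoring times are grouped by nominal visit (Week 4, Week 12/EoT), with early EoT and unscheduled samples assigned by a stated window; alternatively, an interval-censored estimator is used.*

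This also settles what counts as post-baseline data. The grouping must be adopted together with the new censoring date, for the reason shown in step 5. The cost is a short SAP edit, slightly more date programming and coarser event times. No new data are needed.

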4.5.3.3 Vital Signs

Vital sign (pulse rate, systolic blood pressure and diastolic blood pressure) will be taken at screening, week 4 and week 12/EoT, and measurements maybe repeated in case of abnormal results. If more than 1 measurement are available on the same date, the average will be calculated and summarized descriptively including the change from baseline by visit and study treatment.

4.5.3.4 Electronic Columbia-Suicide Severity Rating Scale (eC-SSRS)

Suicidal ideation and behavior will be monitored by eC-SSRS questionnaire.

Version 2.0 Page: 39 of 57

The eC-SSRS assesses lifetime suicidality during an initial baseline evaluation, and then prospectively monitors ideations and behaviors at subsequent follow-up assessments. The eC-SSRS assesses the severity and frequency of suicidal ideation and behavior.

eC-SSRS outcomes will be summarized by study treatment for each visit (baseline, week 4 and 12) using descriptive statistics.

4.5.3.5 Pregnancy Test

Pregnancy test results will be listed.

4.6 Other Analyses

Other pre-specified objectives in this study are:

- To evaluate variability in exposure in relation to the efficacy and safety for elinzanetant
- To further investigate the study intervention and similar compounds (e.g., mode-of-action-related effects, safety) and to further investigate pathomechanisms deemed relevant to sleep disturbances associated with menopause.
- To investigate the efficacy of elinzanetant on sleep disturbance associated with menopause determined by Sleepiz One+

These will be evaluated accordingly by:

- Systemic exposure of elinzanetant in plasma via sparse PK sampling
- Various biomarkers (e.g., diagnostic, safety, pharmacodynamic, monitoring, or potentially predictive biomarkers)
- Parameters captured remotely and continuously at home by Sleepiz One+ including but not limited to e.g., WASO, TST, SE

4.6.1 Pharmacokinetics

PK analyses will be described in a separate document and the results will be presented outside of the CSR. Only concentration data will be provided in a listing.

4.6.2 Biomarkers

The analyses of various biomarkers for diagnostic, safety, pharmacodynamic, etc. will be described in a separate document and the results will be presented outside of the CSR.

4.6.3 Sleepiz One+

The analyses of sleep parameters derived from Sleepiz One + monitor will be presented for the SLAS.

The Sleepiz One+ monitor will be provided to participants at screening to continuously collect sleep data at home in addition to the nights of PSG assessment. Parameters derived from Sleepiz One+ to be analyzed will be:

- WASO (mins)
- SE (%)
- TST (hours)

Version 2.0 Page: 40 of 57

- SOL (mins)
- Wake up latency (mins)
- Awakening count
- Average awakening (per hour of sleep)
- Out of bed count
- Time in bed (hours)
- Respiratory irregularity index (RII) (per hour of sleep)
- Heart rate per minute (min, max, mean, median, 10th and 90th percentile)
- Breathing rate per minute (min, max, mean, median, 10th and 90th percentile)

See Section 6.2.2 for more details on the definition of each parameter.

The parameters listed above are provided by the vendor as nightly values. For the analysis, the weekly mean daily value will be used. The mean value for each study week will be calculated using available data during that week as:

For a particular parameter:

total value of the parameter during that week

total number of available days with data for that parameter during that week

Study week will be assigned using the definition in Section 4.1.2 using the start date of the recording as the date of observation. If the start time of the recording is on or before 11:00, then the date of recording – 1 will be used as the date of observation. The mean daily value can be derived if a value is provided for at least 4 out of 7 nights, otherwise the mean daily value will be set as missing. The baseline value will be calculated similarly using all available days during the 14 days prior to starting treatment. A minimum of 7 days should be available for the derivation of the baseline value.

In single cases of concern that data was not transmitted properly during the participant's Sleepiz One+ use at home, the device will be switched on at site for 24 hours (after the participant returns the device) to transmit potentially stored data. Data recorded during this time will not be analyzed or listed. Therefore, data on or after last PSG assessment date + 1 or last treatment date + 1 or EoT visit date (whichever is the latest) will be excluded from the analysis.

The mean daily value and change from baseline in mean daily value for each parameter will be analyzed using descriptive statistics by study treatment and week. The mean daily value and change from baseline over time by study treatment will be shown using line plots.

In addition, the mean daily value from the PSG nights will be summarized descriptively by study treatment and week. The mean value will be calculated using the same rule to calculate the primary endpoint (Section 4.2.1)), i.e., if there are data for both PSG nights, the mean value of the 2 nights will be used; if only 1 night is available, data from that one night will be used.

Version 2.0 Page: 41 of 57

In addition, total compliance on the participant's use of the Sleepiz One+ device for the period of the treatment duration will be summarized using descriptive statistics by study treatment.

Compliance will be derived using the parameter good signal duration (GSD) which measures the daily total duration where the participant is in sight of the device. A participant will be compliant if the GSD has a total duration of at least 4 hours.

The compliance (as a percentage) will be calculated as

100 * number of days during treatment with GSD \geq 4 hours / treatment duration

Treatment duration is defined in Section 4.5.1. If the participant has no Sleepiz One+ data during treatment, the participant will have a compliance of zero.

As well as a measure of compliance of the participant in using the device, GSD is also a measure of the quality of the data received and the subsequent processed metrics. Therefore, the descriptive statistics of the mean daily value and change from baseline in mean daily value for WASO, TST, SE and SOL will be repeated using only nights with $GSD \ge 4$ hours when deriving the mean daily value.

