 To investigate the efficacy of elinzanetant on sleep disturbance associated with menopause determined by Sleepiz One+ 	 Parameters captured remotely and continuously at home by Sleepiz One+ including e.g. WASO, TST, SE 		

The full list of exploratory endpoints will be presented in the SAP.

GAD-7 = General Anxiety Disorder-7, HF = Hot Flash, ISI = Insomnia Severity Index, PGI-C = Patient Global Impression of Change, PGI-S = Patient Global Impression of Severity, PK = Pharmacokinetics, PROMIS SD SF 8b = Patient-Reported Outcomes Measurement Information System Sleep Disturbance Short Form 8b, PSG = Polysomnography, SAP = Statistical analysis plan, SE = Sleep Efficiency, TEAE = Treatment-emergent adverse event, TST = Total Sleep Time,

21 SEP 2023 Page: 22 of 73

WASO = Wakefulness after sleep onset.

Estimands

The primary clinical question of interest for the primary objective is:

What is the difference in mean change from baseline in WASO as measured by PSG at Week 4 comparing elinzanetant to placebo in women with sleep disturbances associated with menopause assuming no study treatment interruption and discontinuation and no use of prohibited concomitant medications impacting sleep?

The attributes of the main estimand for the primary endpoint are as follows:

- Population: Women aged 40–65 with sleep disturbance associated with the menopause, further defined by the key inclusion/exclusion criteria.
- Variable: Change from baseline in WASO measured by PSG at Week 4.
- Treatment: Elinzanetant 120 mg or placebo.
- ICEs and strategies: Important ICEs to consider are listed in Table 3–2.

Table 3-2: Primary Estimand: ICEs and Strategies to Address Them

ICEs	Proposed Strategy	Data Handling Method	Interpretation
Temporary study treatment interruption	Hypothetical	Discard data collected after the ICE	The treatment effect that would be if participants complied with treatment
Premature discontinuation of study treatment	Hypothetical	Discard data collected after the ICE	The treatment effect that would be if participants did not discontinue the randomized treatment
Intake of prohibited concomitant medication having impact on efficacy	Hypothetical	Discard data collected after the ICE	The treatment effect that would be if participants did not take prohibited concomitant medications impacting sleep

ICE = Intercurrent event.

 Population level summary: Mean change from baseline in WASO measured by PSG at Week 4.

4. Study Design

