4.1.1.2 Sleepiz One+

Several parameters of sleep quality will be measured continuously at home and during the nights of the PSG assessments by the Sleepiz One + system from SCR-2 visit through to week 12/EoT visit. See Section 6.2.2 for the list and definition of sleep parameters as measured by Sleepiz One+.

No imputation of missing assessments will be performed for parameters measured by the Sleepiz One +.

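### The Sleepiz One+ endpoint is defined as captured at home, but its baseline and weekly means include sleep-laboratory nights, and an on-time final visit leaves Week 12 missing

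*SAP*

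**What the plan says.** The endpoint is worded as a home measurement in both documents. Protocol Section 3, Table 3-1, has "Parameters captured remotely and continuously at home by Sleepiz One+ including e.g. WASO, TST, SE". SAP 4.6 has "Parameters captured remotely and continuously at home by Sleepiz One+ including but not limited to e.g., WASO, TST, SE".

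The device is handed out at SCR-2, the first PSG visit (Protocol 8.2.1.2), and it runs in the laboratory too: "Several parameters of sleep quality will be measured continuously at home and during the nights of the PSG assessments" (SAP 4.1.1.2).

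SAP 4.6.3 then sets the averaging rules:

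- Weekly value: "The mean value for each study week will be calculated using available data during that week as" the sum over the available days divided by their number. "The mean daily value can be derived if a value is provided for at least 4 out of 7 nights"; otherwise it is missing.
- Baseline window: "The baseline value will be calculated similarly using all available days during the 14 days prior to starting treatment".
- Baseline threshold, stated in the next sentence of that section: "A minimum of 7 days should be available for the derivation of the baseline value".
- End of data: recordings from the day after the last PSG date, the day after the last treatment date or the EoT visit date, whichever is latest, are dropped. The last PSG night is therefore kept.
- The PSG nights are also summarised on their own, as an addition to the weekly means.
- For four parameters, including WASO, the descriptive summaries are repeated on nights with a good signal duration of at least 4 hours.

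No rule removes PSG nights from the baseline or weekly means.

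**The concern.** A laboratory night is not a home night. The participant is away from her own bed and is recorded by PSG, so WASO, time in bed and sleep efficiency may differ for reasons unrelated to treatment. The SCR-2 nights are also the ones on which eligibility was decided: Protocol 5.1, criterion 6, requires mean PSG WASO of at least 30 minutes with neither night below 20. To the extent that Sleepiz WASO follows PSG WASO, nights selected for high values enter the baseline.

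Laboratory nights are also spread unevenly over the averaging windows. Most treatment weeks would be compared with a baseline that is partly laboratory, and the line plots could show a step at a visit week that reflects only the setting. What is at stake is the level and shape of the within-arm curves, and whether the reported quantity is the one that the documents name.

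**Working it through.** **Study weeks.** SAP 4.1.2 uses the SAS CEIL function, places days 1 to 7 in week 0, and ties days 29 and 85 to Weeks 4 and 12. Week = CEIL(day/7) - 1 fits this and is inferred from it: day 7 gives 1 - 1 = 0, day 29 gives 5 - 1 = 4, day 85 gives 13 - 1 = 12. Week 4 is therefore days 29 to 35 and Week 12 is days 85 to 91. All counts below assume complete recording unless stated.

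**Baseline.** The window is days -14 to -1 (there is no day 0) and the device starts at SCR-2. The Schedule of Activities gives day -10 as nominal. Footnote a requires at least 7 days at home between SCR-2 and BL, so the latest first laboratory night is day -9.

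| First SCR-2 night | Nights in window | Laboratory nights | Share |
|---|---|---|---|
| -16 or earlier | 14 | 0 | 0% |
| -15 | 14 | 1 | 7% |
| -14 | 14 | 2 | 14% |
| -10 (nominal) | 10 | 2 | 20% |
| -9 | 9 | 2 | 22% |

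**Week 4.** With the first night on days 29 to 34, the share is 2/7 = 29%. Day 35 puts one night in Week 4 and one in Week 5. Day 36, the end of the +7 window, puts both in Week 5.

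**Shift in within-arm change from baseline.** Let D be laboratory minus home WASO. The documents do not give it; 5 to 20 minutes of either sign is an assumption. The minute figures below are for positive D, and the signs reverse for negative D.

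Shift = (laboratory share in week - laboratory share at baseline) x D

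- Home-only weeks: 0 - 0.200 = -0.20D, or 0 - 0.222 = -0.22D. For D = 5 to 20 this is -1.0 to -4.4 minutes.
- Week 4: 0.286 - 0.222 = +0.06D, or 0.286 - 0.200 = +0.09D. This is +0.3 to +1.7 minutes.
- Step from Week 3 to Week 4: 0.286D, or 1.4 to 5.7 minutes.
- SCR-2 on day -16 or earlier: home-only weeks have no shift and Week 4 shifts by +0.29D.

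**Between-arm difference.** With the same D and the same expected shares in both arms, the shift is identical in each arm and cancels on average. Only chance imbalance in the shares remains.

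**Week 12.** If the first laboratory night is day p, the last night kept is p + 1. For p from 85 to 90, Week 12 holds (p + 1) - 85 + 1 = p - 83 nights, two of them in the laboratory.

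| p | Nights in Week 12 | Home nights | Status under the 4-of-7 rule |
|---|---|---|---|
| 85 | 2 | 0 | missing |
| 86 | 3 | 1 | missing |
| 87 | 4 | 2 | derived, 50% laboratory |
| 88 | 5 | 3 | derived, 40% |
| 89 | 6 | 4 | derived, 33% |
| 90 | 7 | 5 | derived, 29% |

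At p = 91, one of the 7 Week 12 nights is in the laboratory (14%). At p = 92 none is, and both laboratory nights fall in Week 13.

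**With PSG nights excluded.** Baseline keeps 10 - 2 = 8 home nights (9 - 2 = 7 for SCR-2 on day -9), and Week 4 keeps 7 - 2 = 5. A 7-night baseline minimum would then leave room for one missed night or none.

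**The case against.** The SAP says openly that the device records at home and on PSG nights. The sleep diary (SAP 4.4.2) is handled the same way, with weekly means over all available days plus a separate PSG-night summary. A reader can already set the Sleepiz PSG-night summary beside the home-only weeks. The objective is in the other pre-specified group, the device is optional, the analysis is descriptive and the study tests no hypothesis. All of this stands, and it limits the severity. It does not make the calculated quantity the home quantity that both documents name, because the PSG-night summary adds a table without removing those nights from the means.

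A reader might infer more than the documents support:

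- That laboratory nights fall only in baseline and the two visit weeks. The +7 window can move them to Week 5 or 13, an early EoT visit (Schedule of Activities, footnote c) can fall in any week, and a sufficiently early SCR-2 leaves none in baseline.
- That Week 4 is the worst affected. On the nominal schedule its change from baseline is the least affected, because the shares of 29% and 20% largely offset.
- That the treatment comparison is biased. This would need D, or the laboratory shares, to differ by arm, and nothing in the documents suggests that they do.
- That distortion has been shown. D has no source in the documents, so every figure in minutes is conditional.

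It is also fair to object to replacing the planned means. With the 4-night rule kept, that would make Week 12 missing for first nights on days 87 and 88, which now yield a value.

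**Conclusion.** The mismatch between the endpoint as named and the means as calculated is real and can be read directly from the two documents. Its consequence is confined to the within-arm level and the shape of the time course, and its size in minutes depends wholly on the assumed D. It touches no primary or secondary result.

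Week 12 is a separate gap that does not depend on D. When the T3 stay starts on day 85 or 86, the weekly rule gives no Week 12 Sleepiz value, with or without the laboratory nights. The result rests on the inferred week formula and on data ending with the second PSG night. Severity: minor.

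**What to change.** In SAP 4.6.3, keep the planned summaries and add a repeat of the baseline, weekly and change-from-baseline summaries and line plots with PSG nights excluded, in the same way as the existing repeat for good signal duration. Present this version as the at-home result. For it:

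- require at least 4 home nights for baseline and for each week;
- take the end-of-treatment value from the last 7 home nights before the T3 laboratory stay, and label it as such. For a stay starting on day 85 these are days 78 to 84, which is study Week 11, so the overlap should be stated.

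The cost is a filter on known PSG dates, one more set of descriptive outputs, and fewer nights per mean in baseline and the visit weeks. The baseline minimum in this version is also lower than the planned 7, so some baselines will be less precise.
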